10.4.3. ANALYSIS OF THE SECONDARY ENDPOINT(S)

Response proportion as defined in section 10.4.2 will be evaluated for the 1, 3,6, 12, 18 and 24 month follow-up visits using the same technique as described for the primary endpoint.

Spirox Latera™ implant support of lateral wall cartilage (LATERAL-OR) study	Version 2.0
SPI-CP-301	September 7, 2017

Change in nasal airway obstruction from baseline at 1,3, 6, 12, 18 and 24 months post-procedure as reported by subjects on a VAS 0-100 mm scale (0= no difficulty breathing through nose; 100mm=not-able to breathe through nose) will be analyzed using a mixed model for repeated measures (MMRM). Least-square mean change from baseline and corresponding 95% confidence intervals will be reported. Baseline VAS score will be analyzed in a separate model, including decongestant use as a covariate. Decongestant use will be considered at baseline only to visualize the turbinate contribution to overall obstruction, thus no decongestant VAS will be assessed at the follow-up visits.

Results from the subject satisfaction questionnaire will be tabulated at 6 months. Sensitivity analyses for missing data will be described in the SAP.

10.4.4. SAFETY ANALYSES

Two analysis sets will be used to *summarize* adverse events. The ITT analysis set will be used to summarize acute adverse events (through 1 month post procedure), and the mITT analysis set will be used to summarize adverse events over the entire duration of follow-up. The primary safety reporting time-point is 6 months post-implant.

The overall incidence (i.e., number and percent of subjects with 1 or more adverse event in each class) of adverse events, serious adverse device events, serious adverse events, fatal adverse events, and device related events (e.g., possibly, probably or definitely related) will be calculated for the acute phase, through 6 months post-procedure and for the entire duration of follow-up. The overall incidence of mild, moderate and severe events will be calculated by considering the most severe event for each subject.

In addition, the overall incidence for each adverse event type will be calculated. The adverse event types will be classified according to the following categories:

- Excessive Inflammation
- Significant Foreign body sensation
- Excessive Pain or discomfort
- Infection
- Implant Extrusion, defined as body rejection of implants
- Implant Retrievals, defined as surgeon or subject initiated removal of implants not associated with body rejection of implant
- Implant bent or fractured
- Implant loose
- Implant migration
- Skin irritation
- Hematoma
- Unintended perforation of the skin
- Other

10.4.5. ADHERENCE AND RETENTION ANALYSES

Protocol deviations will be tabulated. Baseline demographic and medical history will be tabulated by whether the 6 month NOSE score data are available or missing to identify potential systematic differences between subjects with and without 6 month follow-up scores.

Spirox Latera™ implant support of lateral wall cartilage (LATERAL-OR) study	
SPI-CP-301	S

10.4.6. BASELINE DESCRIPTIVE STATISTICS

Baseline characteristics, including demographic characteristics, medical history, patient-reported outcomes and physical measurements will be summarized using descriptive statistics.

10.4.7. PLANNED INTERIM ANALYSES

No interim analyses with *formal* stopping implications will be performed, though changes in NOSE score may be aggregated to facilitate sample size calculations for future studies.

10.4.7.1. SAFETY REVIEW

All adverse events will be reviewed by the Medical Monitor. For any reported SAE, the Medical Monitor and Scientific Advisory Board members will review the event and issue a recommendation.

The study sponsor will be responsible for notifying FDA of SAEs pursuant to the applicable MDR reporting requirements 21 CFR 803.

10.4.7.2. EFFICACY REVIEW

No interim analyses with formal stopping implications will be performed, though changes in NOSE score may be aggregated prior to database lock to facilitate sample size calculations for future studies. As there is no opportunity to stop early for efficacy or to alter the study design based on this calculation, there will be no type 1 error adjustment for this analysis.

10.4.8. ADDITIONAL SUB-GROUP ANALYSES

Response percentage, change in NOSE scores and other variables including satisfaction will also be evaluated in the following subgroups:

- Turbinate reduction method: radiofrequency versus mechanical
- Time-dependent presence or absence of allergic rhinitis
- Nasal geometry factors
 - Nose length (above or below median)
 - Nose width (above or below median)
 - Categorical skin thickness

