10.4.9. MULTIPLE COMPARISON/MULTIPLICITY

No formal type 1 error adjustment will be made for the analysis of secondary and exploratory endpoints. All endpoints except for the primary endpoint should be considered supportive, and inference should be drawn with caution.

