10.5. SAMPLE SIZE

The primary study hypothesis is a superiority comparison to a target proportion:

Null Hypothesis H₀: the proportion of responders at 6 months is =0.50, versus Alternative Hypothesis H_A: the proportion of responders at 6 months is \neq 0.50

See section 10.4.2 for the definition of response. This hypothesis will be evaluated using an exact test.

In order to have > 90% power to rule out a response rate \leq 50% at a 5% (2-sided) significance level, assuming a true response rate of 66%, 150 subjects with 6 month follow-up are needed. Assuming about 10% drop-out rate, up to 170 subjects will be enrolled. All mITT subjects will be used for this comparison, regardless of protocol deviations.

The assumed response rate is the minimum value expected to be consistent with previous trials, where an 80% response rate at 6 months was observed.

Sample size calculations were performed using the package RCTDesign for R version 3.2.3.

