### SAMPLE SIZE JUSTIFICATION

The primary statistical hypothesis will be evaluated using an exact test. In order to have > 90% power to rule out a response rate  $\leq$  50% at a 5% (2-sided) significance level, assuming a true response rate of 66%, 120 subjects with 6 months of follow-up are needed. Assuming a 20% drop-out rate, at least 150 subjects (and up to 170 subjects) will be enrolled. A 66% response rate is the minimum response rate that is consistent with a previous trial, where an 80% response rate at 6 months was observed.

Sample size calculations were performed using the package RCTDesign for R, version 3.2.3.

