### 3.2.2 Nose Demographics

Nose demographics will be reported in a similar manner for the ITT (or mITT) analysis sets. Continuous variables include days since endoscopy, nose length, nose bone length, nose height and nose width.

The following categorical variables will be summarized (number and percentage):

- Nose Skin Thickness: Thin, Normal, Thick
- Reason Endoscopy Not Recorded
- Presence of Deviated Septum
- Presence of Inferior Turbinate Hypertrophy
- Modified Cottle Results (by side)

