### 4.5 EXPLORATORY EFFICACY ENDPOINTS

Additional endpoints of interest include:

- Index procedure resource utilization: Anesthesia, procedure time and time to discharge.
- Follow up resource utilization: Nasal airway obstruction related return visits and medication utilization.
- Subject satisfaction questionnaire at 1, 3 and 12 months.
- Degree of nasal way obstruction as reported by subjects on the VAS scale at baseline with decongestant use.
- Endoscopic lateral wall insufficiency score per side21 at baseline and 6 months

- 3-D camera lateral wall motion assessment per side at baseline and 3, 6 and 12 months (at select sites).
- Cosmesis changes from baseline evaluated by Independent Photo Review 3 and 6 months (at select sites).
- Allergic rhinitis status at 1, 3, 6 and 12 months.
- Nasal geometry: length of nose, height and width of nose, skin thickness of lateral wall at baseline.
- Type of turbinate procedure.

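### Nose length and width are related to outcome only through a median split, and the SAP gives no method linking nasal geometry to outcome; an exploratory model on the measured values would use the data better.

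*Protocol*

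**What the plan says.** Protocol 10.4.8 introduces its additional subgroups with "Response percentage, change in NOSE scores and other variables including satisfaction will also be evaluated in the following subgroups". The nasal geometry entries are "Nose length (above or below median", "Nose width (above or below median" and skin thickness in categories. The measurements come from the baseline nasal exam (Protocol 7.2.6).

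The SAP mentions geometry in two places:

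- SAP 3.2.2, as a baseline description: "Continuous variables include days since endoscopy, nose length, nose bone length, nose height and nose width". Skin thickness is tabulated as thin, normal or thick.
- SAP 4.5, as an exploratory endpoint: "Nasal geometry: length of nose, height and width of nose, skin thickness of lateral wall at baseline". No analysis method is attached.

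SAP 4.3 lists the subgroups for the primary endpoint: investigator, type of procedure and turbinate reduction method. Geometry is not among them.

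On inferential status, Protocol 10.4.9 says "All endpoints except for the primary endpoint should be considered supportive, and inference should be drawn with caution". Protocol 4.2.3 presents the exploratory endpoints as informational only.

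**The concern.** The plan records nose length and width on a continuous scale, describes them on that scale, and drops the scale only when relating them to outcome. After a median split, two subjects just either side of the cut count as different, while the smallest and the middling noses in the lower half count as the same. The cut point is also whatever this sample's median turns out to be, so a later study cannot reuse it.

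What is at stake is the precision of an exploratory estimate. The implant comes in one overall length, 24 mm (Protocol 6.2), so whether response varies with nose size is a natural question, and the data to address it are already being collected. Protocol 10.1 leaves analysis detail to the SAP, and the SAP does not supply it here.

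**Working it through.** **1. The plan's own sample-size figures.** The documents give no figure for the geometry subgroups, so the only stated quantities to reproduce are the evaluable numbers.

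- Protocol 10.5: "at a 5% (2-sided) significance level, assuming a true response rate of 66%, 150 subjects with 6 month follow-up are needed". Exact binomial, null 0.50: with n = 150 the upper rejection limit is 88 or more responders, upper-tail alpha 0.0204, power at 66% = 97.5%. Enrolment: 150 / (1 − 0.10) = 167, consistent with up to 170.
- SAP sample size justification: "120 subjects with 6 months of follow-up are needed". With n = 120 the limit is 72 or more, upper-tail alpha 0.0177, power 93.0%.

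Both meet the claim of more than 90% power. Both are carried forward as the number of subjects available for the geometry analysis.

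**2. Information kept by a median split.** For a linear effect of X, the relative efficiency of the split is the squared correlation between X and the indicator I that X exceeds its median. I has standard deviation 0.5. For a standard normal X:

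- Cov(X, I) = 1/√(2π) = 0.399
- correlation = 0.399 / 0.5 = 0.798
- information kept = 0.798² = 2/π = 0.637
- information lost = 1 − 0.637 = 0.363, about 36%

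Equivalent numbers on the measured scale: 150 × 0.637 = 95.5, and 120 × 0.637 = 76.4.

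**3. Dependence on the distribution.** The documents give no distribution for nose length or width. Repeating step 2 with other shapes, effect still linear:

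| Shape of X (assumed) | Information lost |
|---|---|
| Uniform | 25% |
| Normal | 36% |
| Lognormal, log SD 0.15 | 38% |
| t, 5 df | 46% |
| Lognormal, log SD 0.5 | 48% |
| Laplace | 50% |

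**4. Check on the two outcomes.** Effect sizes here are assumed. The response rates are the protocol's planning value (66%) and the earlier trial's observed value (80%). For the binary outcome: 3,000 simulated trials per setting, n = 150, one normal predictor, logistic likelihood-ratio test at 5%.

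| Response rate | Odds ratio per SD | Power, measured | Power, split |
|---|---|---|---|
| 66% | 1.5 | 64% | 44% |
| 66% | 2.0 | 97% | 86% |
| 80% | 1.5 | 51% | 34% |
| 80% | 2.0 | 89% | 73% |

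The information lost in the simulated settings was 35% to 38%, in line with step 2. For NOSE change with an assumed correlation of 0.20, the split reduces the correlation to 0.20 × 0.798 = 0.160, and noncentral-t power at n = 150 falls from 70% to 50%. Power serves here only as a yardstick for lost precision, because the plan contains no test of geometry.

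**The case against.** The strongest reply is that this analysis carries no formal weight. Protocol 10.2 states no hypothesis beyond the primary one, SAP 4.1.1 makes other p-values descriptive, and SAP 4.3 reports its subgroups as proportions with exact confidence intervals. This stands: no planned test loses power, and the primary result, sample size and safety reporting are untouched. It does not remove the point, because an analysis without a test is worth only the precision of its estimate, and the split reduces that.

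A second reply is that the 36% rests on assumptions. This also stands. A true step at the median would favour the split, and a fixed-length implant could equally suggest a threshold or a non-monotone pattern. Nothing in the documents points to any particular shape, or gives a figure for any effect of nose size. That argues for a non-linearity check alongside the linear term.

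Third, a joint model of length and width would not deliver the gain calculated above, which is for one predictor. With two correlated predictors, the information on each scales by 1 − r²; at an assumed r of 0.5 that is 0.75. Separate models avoid this.

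A reader might also infer more than the documents support:

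- *That the SAP has no method for geometry of any kind.* SAP 3.2.2 summarises it at baseline. What is missing is a method relating it to outcome.
- *That SAP 4.3 withdraws the median-split analysis.* That section covers subgroups for the primary endpoint only, while Protocol 10.4.8 also covers NOSE change and satisfaction. The documents leave open whether the geometry analysis is run.
- *That all of nasal geometry is affected.* Skin thickness is recorded in categories and nose height is not a listed subgroup, so neither is split at a median.

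**Conclusion.** The point holds as a minor improvement to an exploratory analysis. The only planned link between outcome and nose length or width is a split at the sample median, and the SAP neither repeats that analysis nor replaces it.

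For a near-normal measure with a linear effect, the cost is about 36% of the information: 150 evaluable subjects are worth about 95, or 120 about 76. Both conditions are assumptions. Varying the distribution alone moves the loss between 25% and 50%, and a sufficiently step-like effect could reverse the comparison. The loss should therefore be quoted as conditional and not as a property of this trial's data.

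**What to change.** In the SAP, state whether the geometry analysis of Protocol 10.4.8 will be run. If so, specify:

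- a logistic model of 6-month response and a linear model of NOSE change on measured nose length and, in separate models, on measured nose width;
- the effect per mm, or per SD with the SD stated, with a 95% confidence interval. The documents do not give the unit of measurement, so name it;
- a spline or quadratic term as a check for non-linearity;
- skin thickness kept in its recorded categories;
- results labelled descriptive, with the median-split table kept for display only.

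The cost is SAP wording and a little extra analysis work. No additional data, visits or subjects are needed. The models do bring in a linearity assumption, which the spline or quadratic check addresses.

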10.4.9. MULTIPLE COMPARISON/MULTIPLICITY

No formal type 1 error adjustment will be made for the analysis of secondary and exploratory endpoints. All endpoints except for the primary endpoint should be considered supportive, and inference should be drawn with caution.

10.4.10. TABULATION OF INDIVIDUAL RESPONSE DATA

Listings of adverse events may be produced.

10.4.11. EXPLORATORY ANALYSES

Cosmesis changes from baseline to 3 month and 6 months, evaluated by Independent Photo Review at 2 sites only, will also be tabulated.

Version 2.0 eptember 7, 2017

Spirox Latera™ implant support of lateral wall cartilage (LATERAL-OR) study	Version 2.0
SPI-CP-301	September 7, 2017

Endoscopic lateral wall insufficiency score is a 3-level, categorical variable, which will be evaluated for each side separately. Baseline and 6 month post-baseline scores will be cross-tabulated, and the proportion with improvement will be calculated.

Response percentage, change in NOSE scores and other variables including satisfaction will also be evaluated by type of procedure (implant alone versus combinations with septoplasty and/or turbinate reductions).

Resource use will also be summarized.

10.5. SAMPLE SIZE

The primary study hypothesis is a superiority comparison to a target proportion:

Null Hypothesis H₀: the proportion of responders at 6 months is =0.50, versus Alternative Hypothesis H_A: the proportion of responders at 6 months is \neq 0.50

See section 10.4.2 for the definition of response. This hypothesis will be evaluated using an exact test.

In order to have > 90% power to rule out a response rate \leq 50% at a 5% (2-sided) significance level, assuming a true response rate of 66%, 150 subjects with 6 month follow-up are needed. Assuming about 10% drop-out rate, up to 170 subjects will be enrolled. All mITT subjects will be used for this comparison, regardless of protocol deviations.

The assumed response rate is the minimum value expected to be consistent with previous trials, where an 80% response rate at 6 months was observed.

Sample size calculations were performed using the package RCTDesign for R version 3.2.3.

10.6. MEASURES TO MINIMIZE BIAS

This is a single arm, open label study. Randomization and blinding are not used.

11. SOURCE DOCUMENTS AND ACCESS TO SOURCE DATA/DOCUMENTS

Each participating site will maintain appropriate medical and research records for this trial, in compliance with ICH E6 and regulatory and institutional requirements for the protection of confidentiality of participants. Each site will permit authorized representatives of the study sponsor and regulatory agencies to examine (and when permitted by applicable law, to copy) clinical records for the purposes of quality assurance reviews, audits, and evaluation of the study safety, progress, and data validity. Source data includes all information, original records of clinical findings, observations, or other activities in a clinical trial necessary for the reconstruction and evaluation of the trial. Examples of these original documents and data records include, but are not limited to, hospital records, clinical and office charts, laboratory notes, memoranda, participants' memory aids or evaluation checklists, recorded data from automated instruments, copies or transcriptions certified after verification as being accurate and complete, microfiches, photographic negatives, microfilm or magnetic media, x-rays, and participant files and records kept at the pharmacy, at the laboratories, and medico-technical departments involved in the clinical trial. Sponsor will provide Source Documents to the sites.

For each subject consented, the inclusion/exclusion source documentation must be signed by the investigator or authorized delegate from the trial staff. If a subject withdraws from the study, the reason

Spirox Latera™ implant support of lateral wall cartilage (LATERAL-OR) study	Version 2.0
SPI-CP-301	September 7, 2017

must be noted on the Study Exit eCRF. If a Subject is withdrawn from the study because of a treatmentlimiting adverse event, thorough efforts should be made to clearly document the outcome.

All forms shall be filled out using indelible ink and must be legible. Errors shall be crossed out but not obliterated and correction inserted and the change initialed and dated by the investigator or authorized delegate. The investigator shall ensure accuracy, completeness, legibility and timeliness of the data reported to the sponsor in the eCRF and in all required reports.

Each investigator/institution agrees that they will permit trial-related monitoring, audits, IRB review and regulatory inspections by providing direct access to source data and/or documents.

12. QUALITY ASSURANCE AND QUALITY CONTROL

Regular monitoring will be performed according to ICH-GCP. See also Section 9, Clinical Monitoring.

Quality Control (QC) procedures will be implemented beginning with the data entry system and data QC checks that will be run on the database will be generated. Any missing data or data anomalies will be communicated to the site(s) for clarification/resolution.

Following written SOPs, the monitors will verify that the clinical trial is conducted and data are generated, documented (recorded), and reported in compliance with the protocol, GCP, and the applicable regulatory requirements (e.g., Good Manufacturing Practices (GMP)).

The investigational site will provide direct access to all trial related sites, source data/documents, and reports for the purpose of monitoring and auditing by the sponsor, and inspection by local and regulatory authorities.

13. ETHICS/PROTECTION OF HUMAN SUBJECTS

13.1. ETHICAL STANDARD

The site PI will ensure that this study is conducted in full conformity with Regulations for the Protection of Human Subjects of Research codified in 45 CFR Part 46, 21 CFR Part 50, 21 CFR Part 56, and/or the ICH E6 and the Declaration of Helsinki.

13.2. INSTITUTIONAL REVIEW BOARD

The protocol, informed consent form(s), recruitment materials, and all participant materials will be submitted to the IRB for review and approval. Approval of both the protocol and the consent form must be obtained before any participant is enrolled. Any amendment to the protocol will require review and approval by the IRB before the changes are implemented to the study. All changes to the consent form will be IRB approved; a determination will be made regarding whether previously consented participants need to be reconsented.

13.3. INFORMED CONSENT PROCESS

13.3.1. CONSENT AND OTHER INFORMATIONAL DOCUMENTATION PROVIDED TO PARTICIPANTS

Consent forms describing in detail the study device, study procedures, and risks are given to the participant and written documentation of informed consent is required prior to starting study-related procedures. Sitespecific Informed Consent Form will be submitted with this protocol for IRB review and approval. Spirox Latera[™] implant support of lateral wall cartilage (LATERAL-OR) study SPI-CP-301

13.3.2. CONSENT PROCEDURES AND DOCUMENTATION

Informed consent is a process that is initiated prior to the individual's agreeing to participate in the study and continues throughout the individual's study participation. Potential risks and benefits of participation will be discussed with the participants. Consent forms will be IRB-approved and the participant will be asked to read and review the document. The investigator will explain the research study to the participant and answer any questions that may arise. All participants will receive a verbal explanation in terms suited to their comprehension of the purposes, procedures, and potential risks of the study and of their rights as research participants. Participants will have the opportunity to carefully review the written consent form and ask questions prior to signing.

The participant will sign the informed consent document prior to any procedures being done specifically for the study. The participants may withdraw consent at any time throughout the course of the trial. A copy of the informed consent document will be given to the participants for their records. The rights and welfare of the participants will be protected by emphasizing to them that the quality of their medical care will not be adversely affected if they decline to participate in this study.

A Subject Research Participation Note will be filed in the subject's medical record, documenting that the informed consent process occurred and the subject voluntarily provided written informed consent to participate in the study.

